10.3. Effectiveness analysis

Data name	Derivation and calculation methods	
Remission	When the CDAI score is <150, the case is regarded as remission.	
WPAI	
Q1 Do you work now? Yes, no
 
Q2 How many hours did you leave the work due to problems related to Crohn's disease over the past 7 days? () hour(s)
 
Q3 How many hours did you leave the work for a reason other than Crohn's disease such as holidays or hours for which you were off to participate in this survey over the past 7 days? () hour(s)
 
Q4 How many hours did you actually work for the past 7 days? () hour(s)
 
Q5 How much productivity was affected by Crohn's disease while you were working over the past 7 days? 0: Crohn's disease did not affect the work. 10: Crohn's disease completely interrupted the work. Based on the above, your score between 0 to 10. ()
 
Q6 How much did Crohn's disease affect various daily activities except your job over the past 7 days? ()
	

Data name	Derivation and calculation methods		
		
0: Crohn's disease did not affect daily activities.
 
10: Crohn's disease completely interrupted daily activities.
 
Based on the above, your score between 0 to 10.
	

- Absenteeism (%)

Calculate it with the following formula based on the questions (Q1 to Q6) on the above table:

$$[Q2 / (Q2 + Q4)] \times 100$$

- Presenteeism (%)

Calculate it with the following formula based on the questions (Q1 to Q6) on the above table:

$$(Q5 / 10) \times 100$$

- Overall work impairment (%)

Calculate it with the following formula based on the questions (Q1 to Q6) on the above table:

$$\{ Q2 / (Q2 + Q4) + [1 - Q2 / (Q2 + Q4)] \times (Q5 / 10) \} \times 100$$

- Activity Impairment (%)

Calculate it with the following formula based on the questions (Q1 to Q6) on the above table:

$$(Q6 / 10) \times 100$$

11. How to stratify data

Data	How to stratify
Dosage and administration	160mg→80mg→40mg once every two weeks, other
Dosing frequency (times)	≥1 and <4, ≥4 and <13, ≥13 and <26, ≥26 and <39, ≥39 and <52, ≥52 and <65, ≥65 and <78, ≥78
Total dose (mg)	<500mg, ≥500mg and <1000mg ≥1000mg and <2000mg ≥2000mg and <3000mg ≥3000mg, Unknown

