12.1. Assessment period for CDAI, WPAI, CRP and non-intestinal conditions

Time allowance of assessment period with the first administration date of Humira as 1 is as follows:

Assessment period	Time Allowance(Day)
At the first administration	- 1 (scheduled date 1)
Week 4 of administration	15 - 43 (scheduled date 29)
Month 3 of administration	71 - 99 (scheduled date 85)
Month 6 of administration	169 - 197 (scheduled date 183)
Year 1 of administration	337 - 393 (scheduled date 365)
Year 1 and Month 6 of administration	519 - 575 (scheduled date 547)
Year 2 of administration	701 - 757 (scheduled date 729)
Year 2 and Month 6 of administration	883 - 939 (scheduled date 911)
Year 3 of administration	1065 - 1121 (scheduled date 1093)
At final assessment	Final assessment of each patient no matter whether the each assessment period is within Time Allowance.

The data for analysis should derive from the date closest to the scheduled date within Time Allowance. If there are more than one data dated on the same day, select the worst value.

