13.3. Effectiveness

“3.1 CDAI remission rate at the final assessment (CDAI<150)”

Patients for analysis: patients in the effectiveness analysis group

Analysis objective: to show the remission rate of CDAI at the final assessment

Analysis items: calculate the number of target patients, the percentage to the number of patients who achieved a remission at the final assessment and to the number of target patients, and the percentage to the number of patients who failed to achieve a remission and to the number of target patients.

Note: Follow “12.1 Assessment period for CDAI, WPAI, CRP and non-intestinal conditions” for Time Allowance of the final assessment periods.

“3.2.1.1 Changes in Crohn’s disease activity index (CDAI) since the administration was started (Observed Case)”

Patients for analysis: patients in the effectiveness analysis group

Analysis objective: to show changes in CDAI and CDAI at each assessment period.

Analysis items: Calculate the number of target patients, the mean and standard deviation of CDAI,

the mean and standard deviation of changes in CDAI for each assessment period, and conduct a paired-t test which compares the values at the initial administration. In addition, calculate the mean days from the first administration date to the final assessment date and the \pm standard deviation.

Note: Follow “12.1 Assessment period for CDAI, WPAI, CRP and non-intestinal conditions” for Time Allowance of the final assessment periods. The analysis covers only the patients with the assessment at the first administration and thereafter.

“3.2.1.2 Changes in Crohn’s disease activity index (CDAI) since the administration was started (Observed Case)”

Patients for analysis: the patients in the effectiveness analysis group whose CDAI was a remission (≥ 150) after they were started on Humira.

Analysis objective: to show changes in CDAI and the CDAI at each assessment period of patients whose CDAI failed to achieve a remission when the administration was started.

Analysis items: Calculate the number of target patients, the mean and standard deviation of CDAI, the mean and standard deviation of changes in CDAI for each assessment period, and conduct a paired-t test which compares the values at the initial administration. In addition, calculate the mean days from the first administration date to the final assessment date and the \pm standard deviation.

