Note: Follow “12.1 Assessment period for CDAI, WPAI, CRP and non-intestinal conditions” for Time Allowance of the final assessment periods. The analysis covers only the patients with the assessment at the first administration and thereafter.

“3.2.2.1 Changes in the remission rate at each point (CDAI<150) (Observed Case)”

Patients for analysis: patients in the effectiveness analysis group

Analysis objective: to show the remission rate of CDAI at each assessment period.

Analysis item: Calculate the number of target patients, the percentage to the number of patients who achieved a remission and the number of target patients, 95%CI of the remission rate, and conduct a McNemar test for the first administration per assessment period.

Note: Follow “12.1 Assessment period for CDAI, WPAI, CRP and non-intestinal conditions” for Time Allowance of the final assessment periods. The analysis covers only the patients with the assessment at the first administration and thereafter.

For the confidence interval, use the Clopper-Pearson’s confidence interval.

“3.2.2.3 Changes in the remission rate at each point (CDAI<150) (Observed Case)”

Patients for analysis: the patients in the effectiveness analysis group whose CDAI was a remission (≥ 150) after they were started on Humira.

Analysis objective: to show the remission rate of CDAI at each assessment period of patients whose CDAI failed to achieve a remission when the administration was started.

Analysis item: Calculate the number of target patients, the percentage to the number of patients who achieved a remission and the number of target patients, 95%CI of the remission rate, and conduct a McNemar test for the first administration per assessment period.

Note: Follow “12.1 Assessment period for CDAI, WPAI, CRP and non-intestinal conditions” for Time Allowance of the final assessment periods. The analysis covers only the patients with the assessment at the first administration and thereafter.

For the confidence interval, use the Clopper-Pearson’s confidence interval.

“3.2.4.2 Endoscopy results during administration (small intestine: active phase/remission phase)”

Patients for analysis: patients in the effectiveness analysis group

Analysis objective: to show endoscopy results (small intestine) at each assessment period.

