Note: Follow “12.2 Assessment period for endoscopy results” for Time Allowance of assessment period. The analysis covers only the patients with the data showing that endoscopy for small and large intestines was done on the same day at the first administration and thereafter in the effectiveness analysis group.

“3.2.6.2 Changes in WPAI:CD since the administration was started (Observed Case)”

Patients for analysis: patients in the effectiveness analysis group

Analysis objective: to show WPAI at each assessment period.

Analysis items: Calculate the number of target patients and the summary statistics of WPAI for each assessment period, and conduct a paired-t test which compares the values at the initial administration.

Note: Follow “12.1 Assessment period for CDAI, WPAI, CRP and non-intestinal conditions” for Time Allowance of the final assessment periods. The analysis covers only the patients with the WPAI assessment at the first administration and thereafter in the effectiveness analysis group.

“3.2.7.2 Changes in CRP level since the administration was started (Observed Case)”

Patients for analysis: patients in the effectiveness analysis group

Analysis objective: to show CRP levels at each assessment period.

Analysis items: Calculate the number of target patients and the summary statistics of CRP for each assessment period, and conduct a paired-t test which compares the values at the initial administration.

Note: Follow “12.1 Assessment period for CDAI, WPAI, CRP and non-intestinal conditions” for Time Allowance of the final assessment periods. The analysis covers only the patients with the CRP assessment at the first administration and thereafter in the effectiveness analysis group.

“3.2.7.3 Remission rate at the final assessment in patients who achieved a remission of CDAI at Week 4 of administration”

Patients for analysis: Patients in the effectiveness analysis group (the patients who did not achieve a remission (≥ 150) when the administration was started but achieved the remission (< 150) at Week 4 of administration in CDAI)

Patients for analysis: to show the remission rate of CDAI at the final assessment regarding the patients who did not achieve a remission (≥ 150) when the administration was started but achieved the remission (< 150) at Week 4 of administration.

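### SAP charts 3.2.1.2 and 3.2.2.3: the population line calls CDAI ≥150 a remission and times it after treatment start, against SAP 10.3 and the charts' own objective

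*SAP*

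**What the plan says.** SAP 10.3 sets the rule for the whole plan: "When the CDAI score is <150, the case is regarded as remission".

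In SAP 13.3, charts 3.2.1.2 (CDAI and its change by visit) and 3.2.2.3 (remission rate by visit) use the same population line. It opens with "the patients in the effectiveness analysis group whose CDAI was a remission", and the full condition is "whose CDAI was a remission (≥ 150) after they were started on Humira". The objective line just below it, in both charts, describes "patients whose CDAI failed to achieve a remission when the administration was started".

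Chart 3.2.7.3 needs the same baseline condition and words it consistently: "the patients who did not achieve a remission (≥ 150) when the administration was started".

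SAP 12.1 gives the first administration its own CDAI window, ending on Day 1. The next window, Week 4, opens on Day 15.

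**The concern.** The population line conflicts with the rest of the SAP on two counts. It attaches the word remission to a value that SAP 10.3 classes as non-remission, and it moves the condition from the start of treatment to some time afterwards.

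The timing matters more. A filter on CDAI after treatment start selects patients on the variable that the chart then reports. Requiring a later value of ≥150 removes patients in sustained remission and admits patients who were in remission at the start and later flared. Following the word remission instead keeps responders. Either way the remission rates, CDAI changes and tests would describe a group chosen by its outcome.

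Protocol section 3 sets no minimum CDAI for entry, and SAP section 11 has a baseline stratum below 150. The whole-group charts 3.2.1.1 and 3.2.2.1 can therefore include patients already in remission at the start. Chart 3.2.7.3 covers only Week 4 remitters, and chart 3.4.1 only the final assessment. Charts 3.2.1.2 and 3.2.2.3 are thus the only visit-wise CDAI summaries restricted to active disease at start. SAP 3.1 says that the plan supports the regulatory report and the re-examination application.

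**Working it through.** The plan states no rate, sample size or power for these two charts, so there is no figure to reproduce. The check is a comparison of text, followed by an illustration of whether the choice of filter matters.

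**Text comparison**

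| Source in SAP | State named | Value | Time |
|---|---|---|---|
| 10.3 | remission | <150 | any |
| 3.2.1.2 and 3.2.2.3, population line | remission | ≥150 | after start |
| 3.2.1.2 and 3.2.2.3, objective line | not in remission | none given | at start |
| 3.2.7.3, baseline condition | not in remission | ≥150 | at start |

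The population line departs from the other rows on state and on time. Its value agrees with chart 3.2.7.3 and with the complement of SAP 10.3. So the number is correct for the intended group, and the label and timing are not.

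Two other items in the charts do not settle the matter. The note requires a baseline value and a later value to exist, but does not say which one selects the patient. Chart 3.2.2.3 also asks to "conduct a McNemar test for the first administration per assessment period". In the intended group nobody is in remission at baseline, so one discordant cell is zero by construction. With k later remitters the exact p-value is 2 × 0.5^k: 0.0625 for k = 5 and 0.031 for k = 6. That test suits a group containing some baseline remitters, so it does not point a programmer to the intended filter.

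**Illustration (all inputs assumed; none is in the documents)**

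CDAI at baseline, Week 4 and Year 3 is taken as trivariate normal:
- baseline mean 200 or 250, SD 90
- Week 4 mean 160, SD 80
- Year 3 mean 140, SD 80
- common pairwise correlation 0.3, 0.5 or 0.7
- one million simulated patients per scenario

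The quantity is P(Year 3 CDAI <150 | filter). Unfiltered it is Φ((150 − 140)/80) = Φ(0.125) = 55%, which the simulation returns. The filters are:
- A: baseline ≥150 (the objective line)
- B: ≥150 after start, taken at Week 4
- C: in remission after start, taken as Week 4 <150

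| Baseline mean, correlation | A | B | C | B − A | C − A | Share of B in remission at baseline |
|---|---|---|---|---|---|---|
| 200, 0.3 | 49.2% | 46.3% | 65.5% | −2.9 | +16.3 | 21.3% |
| 200, 0.5 | 45.3% | 40.1% | 73.0% | −5.2 | +27.7 | 15.9% |
| 200, 0.7 | 41.2% | 33.1% | 81.6% | −8.1 | +40.4 | 9.9% |
| 250, 0.3 | 52.1% | 46.3% | 65.6% | −5.8 | +13.5 | 8.6% |
| 250, 0.5 | 50.4% | 40.2% | 73.1% | −10.2 | +22.7 | 5.4% |
| 250, 0.7 | 48.9% | 33.2% | 81.6% | −15.7 | +32.7 | 2.3% |

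Filter B lowers the rate by 3 to 16 points and filter C raises it by 14 to 40. If B is read as ≥150 at either Week 4 or Year 3, the rate is 29% to 36%, which is 12 to 20 points below A. The sign depends on which part of the line is followed.

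**The case against.** The intended population is not in real doubt. The objective line sits directly below the faulty one in both charts, the printed value ≥150 fits it, and chart 3.2.7.3 spells out the same condition. A programmer who follows these gets filter A and no error. The literal line cannot even be programmed alone: it names no visit and no any-or-all rule, so the programmer must look elsewhere, and the objective line is the nearest source. Filter C also requires discarding the printed ≥150.

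Other outputs limit the damage. Charts 3.1, 3.2.1.1 and 3.2.2.1 use the whole effectiveness group. Chart 3.4.1 gives final-assessment remission by baseline CDAI. Chart 1.12 counts baseline CDAI strata, and the sum of the three strata from 150 upward caps the size of the intended group, so a wrong selection could be noticed.

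Most of this stands, and it rules out two stronger readings. A reader might infer that the cut-off is inverted; it is not, because ≥150 is the value for non-remission. A reader might also infer that the reported remission course is wrong; nothing in the documents shows that the line was programmed literally.

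What remains is that the population line is the field that sets the filter, it disagrees with the objective on state and time, and the SAP gives no rule on which line prevails. No other chart supplies the visit-wise course in patients with active disease at start.

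**Conclusion.** The population line of charts 3.2.1.2 and 3.2.2.3 is wrong as written, in its label and its timing, and should be corrected. The evidence is the SAP's own text and needs no assumption.

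The consequence is conditional. Only a literal filter would select on post-treatment CDAI, and the resulting bias could go either way. Its size cannot be derived from the documents; the ranges above rest wholly on assumed means, SDs and correlations and show only that the choice of filter is not trivial. The point does not reach the whole-group effectiveness charts or chart 3.4.1.

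**What to change.** In both charts, replace the population line with: *patients in the effectiveness analysis group whose CDAI was not in remission (≥150) at the first administration, using the section 12.1 window*. This brings the line into agreement with SAP 10.3, the objective lines and chart 3.2.7.3.

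If outputs already exist, check which filter was programmed and rerun the two charts if it was not the baseline one. The number of patients in each chart should not exceed the chart 1.12 count with baseline CDAI ≥150 in the effectiveness group.

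The cost is one line of wording in two charts and a look at the code. No new data are needed.

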Humira® for Subcutaneous Injection

Protocol for Special Investigation

(Long-term treatment for Crohn's Disease patients)

AbbVie GK

Protocol No. P13-170

1. Purpose of the investigation

This special investigation of Humira for Subcutaneous Injection will be conducted to obtain information on the safety (especially profile of malignant tumors and serious infections) and effectiveness in patients with Crohn's disease who are receiving Humira for a long period of time.

2. Target number of patients

(1) Target sample size

A total of 500 patients.

(2) Rationale

The incidence of malignant tumors in clinical studies in CD patients conducted in- and outside Japan prior to the approval of Humira for CD were 1.1% (1/90 patients) and 1.1% (16/1459 patients). Based on these incidences, we plan to investigate 300 patients to detect at least one case of malignant tumor at a probability of 95%, and register 500 patients, since a substantial number of patients will discontinue or withdraw from the investigation.

3. Patients to be investigated

Patients who meet the following criteria at baseline will be evaluated in the investigation:

- (1) Patients with Crohn's disease indicated for Humira treatment with the recommended dosage regimen.
- (2) Patients with no past- or present malignant tumors.
- (3) Patients who are not currently receiving Humira.

4. Number of participating institutions by department

The investigation will be conducted in about 100 eligible institutions.

5. Criteria of participating institutions and investigators

The investigation will be conducted by the institutions and physicians that satisfy the following criteria and have concluded agreements with AbbVie GK. for implementation of the investigation.

(1) Participating institutions

Institutions that satisfy the following criteria will participate in the investigation:

- 1) Institutions that have concluded or will conclude agreement with AbbVie GK. for implementing the all-case investigation of Humira in patients with Crohn's disease
- 2) Institutions where the effectiveness of Humira can be evaluated using Crohn's Disease Activity Index (CDAI) whenever possible.

(2) Participating investigators

Investigators that satisfy the following criteria will participate in the investigation:

- 1) Physicians who have participated in the all-case investigation of Humira in Crohn's disease ^{*1}

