4.3. Target sample size for the survey

500 patients

The incidence of malignant tumour when this drug was approved was 1.1% (1/90) in the domestic clinical study and 1.1% (16/1459) in the overseas clinical study in Crohn's disease-patients, showing that malignant tumour occurred in approximately 1.0% of the patients both in Japan and overseas. Therefore, we have a sample size of approximately 300 patients for this survey to detect at least one patient who develops malignant tumour with a power of 95%. We are going to register 500 patients in view of possible withdrawals and dropouts in the follow-up period.

5. Items to be analyzed and the methods

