9.1. Handling of missing data

The relevant item's definition at Chapter 10 or thereafter defines how to impute data. In addition, for date imputation, follow the table below to impute the dates.

Item	Entry data			Dates after imputation	Replacement
	year	month	day		
Chest X ray, Thoracic CT, other imaging, Tuberculin test, QuantiFeron test, endoscopy	2018	1	null	January 1, 2018	If a date is null, regard it as the first day of the month.
	2018	1	-97	January 1, 2018	If a date is unknown, regard it as the first day of the month.
	2018	1	The first 10 days of a month	January 1, 2018	If a date is any of the first 10 days of a month, regard it as the first day of the month.
CRP	2018	1	null	null	If the date is null, it is regarded as null.
	2018	1	The end of a month	January 31, 2018	If the date is “the end of month”, replace it with the actual end date of the applicable month.
CDAI	null	1	1	null	If a year is null, it is regarded as null.
General (including the items above and WPAI)	-97	-97	-97	null	If a year, a month and a date are all unknown, they are regarded as null.
	null	null	null	null	If a year, a month and a date are all null, they are regarded as null.
	2018	-97	-97	null	If a month and a date are unknown, they are regarded as null.
	2018	null	null	null	If a month and a date are null, they are regarded as null.

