Dose period	the first administration to Week 4 of administration, after Week 4 of administration to Month 3 of administration, after Month 3 of administration to Month 6 of administration, after Month 6 of administration to Year 1 of administration, after Year 1 of administration to Year 1 and Month 6 of administration, after Year 1 and Month 6 of administration to Year 2 of administration, after Year 2 of administration to Year 2 and Month 6 of administration, after Year 2 and Month 6 of administration to Year 3 of administration, Continued as of Year 3 of administration
Reason for discontinuation	Development of adverse event, lack of effectiveness, patient's wish, no visit, others
Sex	Man, women, unknown/not provided
Pregnancy/nursing	Not pregnant/nursing, pregnant, nursing, unknown/not provided
Age (in years)	<15, ≥15 and <65, ≥65, unknown/not provided
Body weight (kg)	<30, ≥30 and <40, ≥40 and <50, ≥50 and <60, ≥60, unknown/not provided
BMI(kg/m ²)	<18.5, ≥18.5 and <25, ≥25 and <30, ≥30, unknown
Duration of illness (in	<2, ≥2 and <5, ≥5 and <10, ≥10, unknown/not provided

Data	How to stratify
years)	
Indication	Crohn's disease, other, unknown/not provided
Allergy history	Without the history, with the history, unknown/not provided
Smoking history	Without the history, with the history, unknown/not provided
Details of smoking history	Smoking, only in the past (not smoking now), unknown
HBs antigen	Not conducted, conducted, unknown/not provided
Tuberculosis-test status	Not conducted, conducted
Complications	Without the history, with the history, unknown/not provided
Detailed classification of complications	Liver disorder, renal disorder, blood disorder, respiratory disorder, others
Other classification of complications	Diabetes mellitus, osteoporosis, malignant tumour, others
Medical history	Without the history, with the history, unknown/not provided
Detailed classification of medical history	Tuberculosis, non-tuberculous mycobacteriosis, interstitial pneumonia, bronchitis bacterial, aplastic anaemia, pancytopenia, malignant tumour, others
Prior medications for Crohn's disease	Without the history, with the history, unknown/not provided
Detailed classification of prior medications for Crohn's disease	Anti-TNF α drug, aminosalicylic acid products, corticosteroid, immunosuppressant, and antibiotics.
Prior treatment for Crohn's disease	Without the history, with the history, unknown/not provided

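### Visit-wise CDAI remission (SAP charts 3.2.2.1 and 3.2.2.3) is observed-case only, so the Year 1 to Year 3 rates are likely overstated as rates among patients who started treatment

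*SAP*

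**What the plan says.** SAP section 13.3, charts 3.2.2.1 and 3.2.2.3, gives for each assessment period the number of patients, the remission rate, a Clopper-Pearson 95% interval and a McNemar test against baseline. The charts are titled "Changes in the remission rate at each point (CDAI<150) (Observed Case"), and each carries the note: "The analysis covers only the patients with the assessment at the first administration and thereafter". I read 3.2.2.3 as restricted to patients with baseline CDAI of 150 or more, as its objective says; its population line is worded inconsistently with that.

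Remission is defined in SAP section 10.3: "When the CDAI score is <150, the case is regarded as remission". SAP section 9.1 says that "Chapter 10 or thereafter defines how to impute data", but neither section 10.3 nor section 12.1 gives a rule for a missing CDAI score. The table in 9.1 deals only with dates.

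Protocol section 8(1) treats stopping Humira, including a suspension of at least 2 months, as the end of the survey for that patient. SAP section 11 begins its list of reasons for discontinuation with "Development of adverse event, lack of effectiveness", followed by patient's wish, no visit and others. Protocol section 2(2) registers 500 patients when 300 are needed, "since a substantial number of patients will discontinue or withdraw from the investigation".

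Three other provisions matter here. Protocol section 8(3) item 9 collects a CDAI when treatment stops. SAP section 12.1 defines a final assessment for every patient, whether or not it falls in a visit window. Chart 3.1 reports remission at that final assessment for the effectiveness group.

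**The concern.** A patient who stops because the drug is not working has no later CDAI and drops out of the numerator and denominator of every later visit. If such patients are in remission less often than those who stay, the visit-wise rate can hold steady or rise because failures have left. The exact interval does not help: it describes sampling error among the patients observed, not the uncertainty from those missing.

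SAP section 3.1 says the results feed the regulatory report and the re-examination application, and section 4.1 sets the aim as effectiveness in patients who used the drug. A Year 3 remission rate with a confidence interval may well be read as the proportion of starters in remission at Year 3. The observed-case label discloses the method. It does not show how far the rate could move.

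**Working it through.** **1. The plan's own figures.** SAP section 4.3 assumes that "malignant tumour occurred in approximately 1.0% of the patients both in Japan and overseas" and has "a sample size of approximately 300 patients for this survey to detect at least one patient" with 95% probability.

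- n = ln(0.05) / ln(1 − 0.010), rounded up, is 299. The probability of at least one case in 300 is 1 − 0.99^300 = 0.951. The figure of about 300 reproduces at 1.0%. At 1.1% the same formula gives 271.
- The step from 300 to 500 corresponds to a loss of 1 − 300/500 = 40%, and 300 / (1 − 0.40) = 500. Neither document states this percentage.

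**2. Does the CDAI taken at stopping reach the visit charts?** Mostly not. By section 12.1, the windows between Day 2 and Day 1064 (the day before the Year 3 window opens) are three of 29 days (Week 4, Month 3, Month 6) and four of 57 days (Year 1 to Year 2.5).

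- In-window days: 3 × 29 + 4 × 57 = 315 of 1063.
- Out-of-window days: 1063 − 315 = 748, or 70%.

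This counts calendar days and does not forecast when patients stop. A stopping value that does fall in a window counts at that visit only.

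**3. Size of the gap.** Let O be the observed-case rate, d the proportion missing, and r the remission proportion among leavers at that time. The rate among all starters is

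R = (1 − d) × O + d × r, so the gap is O − R = d × (O − r).

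O, d and r are all assumptions. I take d = 0.40 from step 1 as an illustration, and O = 0.60:

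| Remission among leavers, r | R = 0.36 + 0.40 × r | Gap (points) |
|---|---|---|
| 0% | 36% | 24 |
| 20% | 44% | 16 |
| 50% | 56% | 4 |
| 60% (same as stayers) | 60% | 0 |

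Other inputs:

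- r = 0, d = 0.40, O = 50% or 70%: R = 30% or 42%, a gap of 20 or 28 points.
- r = 0, O = 60%, d = 0.20 or 0.30: a gap of 12 or 18 points.
- O = 60%, d = 0.40, with a quarter or half of leavers not in remission and the rest matching stayers: a gap of 0.40 × 0.25 × 60 = 6 points or 0.40 × 0.50 × 60 = 12 points.

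**4. What the interval shows.** 180/300 = 60.0% has a Clopper-Pearson 95% interval of 54.2% to 65.6%. 180/500 = 36.0% has 31.8% to 40.4%. The first interval contains the 56% scenario but not the 44% or 36% ones. The denominator of 500 registered patients is for illustration only. A row built on effectiveness-group patients with a baseline CDAI would have a smaller denominator.

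**5. Do other charts supply the missing rate?** Chart 3.1 uses each patient's last CDAI. It pools someone who stopped at Month 3 with someone who completed Year 3, and it can carry forward a remission recorded before an adverse-event stop. It gives no rate at a fixed time. Charts 1.6.3 (Kaplan-Meier continuation) and 1.7 (reasons for discontinuation) are built on the safety group. The remission charts use effectiveness-group patients with a baseline and a later CDAI, so the two cannot be multiplied to obtain a valid rate.

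**The case against.** The strongest reply is that the plan does not lose sight of leavers. CDAI is collected at stopping, the final assessment uses it, and chart 3.1 puts it first among the effectiveness charts. The notes to 3.2.2.1 and 3.2.2.3 also refer to the final-assessment period of section 12.1, so those charts may carry a row that includes leavers with a baseline and any later value. A patient who stops with CDAI of 150 or more is counted there as not in remission. Each visit also shows its number of patients, and continuation and reasons for stopping are tabulated. Remission among patients still treated is a legitimate descriptive quantity, and the label is honest. All of this stands. It makes the final assessment a partial remedy, but it leaves no Year 1, 2 or 3 rate on a fixed denominator.

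Four stronger readings are tempting, and the documents do not support them:

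- **That 40% attrition is planned for.** The figure is only implied by 300/500 in a malignancy-detection rationale. It does not forecast missing CDAI at Year 3.
- **That the rates are certainly overstated.** The direction requires leavers to be in remission less often than stayers. Lack of effectiveness is one of five listed reasons, and the split is not given.
- **That the Year 1 to Year 3 rates are the survey's main effectiveness result.** No primary effectiveness measure is named. Where the SAP needs one result per patient (patient list 1.4, Attachment Form 3, chart 3.4.1), it uses the final assessment.
- **That 36% is the true counterpart of an observed 60%.** It is the extreme case, and both the 60% and the retention are assumed.

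**Conclusion.** The point holds as a worthwhile, inexpensive improvement. Charts 3.2.2.1 and 3.2.2.3 are observed-case only, stopping treatment ends follow-up, no rule covers a missing CDAI, and no chart gives visit-wise remission on a fixed denominator. The Year 1 to Year 3 rates are therefore likely, though not certain, to overstate remission among patients who started.

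With 40% missing and 60% observed remission, the overstatement runs from 0 points (leavers match stayers) to 24 points (no leaver in remission). The planned outputs cannot show where in that range the survey lies at a given visit. The observed-case analysis is not wrong in itself; it needs a clearer label and a companion figure.

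**What to change.** Keep the observed-case rows and label them as remission among patients still treated and assessed. At each visit in charts 3.2.2.1 and 3.2.2.3 add two rows, each with a Clopper-Pearson interval. In both, a patient with a CDAI in the window is counted by that value.

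- **Row (a).** To the observed patients add those who discontinued before the visit for lack of effectiveness or an adverse event, counted as not in remission. Because the SAP lets reasons overlap, either reason is enough. Other patients without a CDAI in the window stay out of this row's denominator, and their number is shown by reason: other discontinuation, or continuing but not measured. The second group needs its own count because protocol section 5(1) expects CDAI only where feasible.
- **Row (b), lower bound.** The denominator is every effectiveness-group patient with a baseline CDAI (for 3.2.2.3, those with baseline CDAI of 150 or more). Every patient without an in-window CDAI is counted as not in remission.

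No new data are needed: the reason for discontinuation is collected under protocol section 8(3) item 13, and SAP section 10.1 derives the final administration date. The cost is a little programming and a less favourable figure beside the observed-case one.
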